Topical analgesic have a place in managing musculoskeletal pain but their scientific efficacy has usually been anecdotal and seldom subjected to investigational scrutiny. These topical agents are relatively safe but may still have adverse effects by virtue of their pharmacological compositions. The use of natural compounds e.g. essential oils from selective herbal extracts have been used by many persons from tropical and subtropical regions for medicinal purposes including pain.

Thus, the objective of this study is to evaluate the efficacy and onset of action of Bonipar, a topical analgesic derived from a variety of essential oils, in controlling pain in patients with acute and chronic musculoskeletal pain, as compared to the topical NSAID, Diclofenac topical solution 1.5%.

Design & Procedures

- Describe the study, providing detail regarding the study intervention (drug, device, physical procedures, manipulation of the subject or the subject's environment, etc.). Discuss justifications for placebo control, discontinuation or delay of standard therapies, and washout periods if applicable. Identify procedures, tests and interventions performed exclusively for research purposes or more frequently than standard of care. Include alternative therapies, concurrent therapies discontinued per protocol, risk benefit ratio, and use of tissue/specimens. Discuss monitoring during washout periods if applicable. Include brief description of follow-up, if any.

This study is a non-inferiority study comparing efficacy and onset of action between the herbal extracts topical solution, Bonipar, and diclofenac sodium topical solution, diclofenac topical solution 1.5% (approved by the FDA as a topical analgesic). Approximately 240 Duke patients will be recruited from Duke Pain Clinic, and selected Duke primary care practices, as well as the Durham VA site. Individuals who report acute (less than 3 months duration) or chronic musculoskeletal pain of any intensity will be considered for enrollment into the study. After obtaining consent, eligible subjects will be will be randomized to receive Bonipar or diclofenac topical solution 1.5%.

For study purposes, diclofenac topical solution 1.5% will be used off-label—that is, it may be used for pain not known to be caused by osteoarthritis. However, this study does not aim to identify a new indication for diclofenac topical solution 1.5%.

Baseline Assessments

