The following baseline assessments will be completed prior to administration of study drug:

- Review of medical history
- Although the risk of serious side effects is low when diclofenac is applied to the skin, pregnant women will be excluded from this study. Urine pregnancy screening will be conducted for all female subjects of childbearing potential.* Women who have a positive pregnancy test would be excluded.
- Limited skin examination and blood pressure measurement. We will exclude patients with SBP > 160 and DBP > 95 at screening.
- Collect pain information such as onset, pain intensity 24 hours prior and immediately before study drug application

*Female subjects are considered "of child-bearing potential" if they (a) are anatomically and physiologically capable of becoming pregnant and (b) they will be, or could possibly be, engaging in sexual activity with males while study interventions that pose the possibility of harm to a fetus are occurring. Note that this time period also includes any time after study activities have ended where the protocol specifies the use of contraception.

Dose, Delivery and Dispensing

After obtaining consent, subjects will be randomized to one of two study groups (Bonipar or diclofenac topical solution 1.5%), utilizing a predetermined randomization schedule in a 1:1 ratio.

The study drug, Bonipar, is stored in an opaque plastic bottle so that the contents may be protected from both direct and indirect sunlight because it is likely that sunlight could result in the degradation and/or decomposition of some of the essential oils contained in Bonipar. For blinding purposes, Diclofenac topical solution 1.5% will be stored in the same opaque plastic bottle. The bottles will be labeled either "Drug A" or Drug B" according to their designation, lot #, BUD (beyond use dating), dosing instructions, and FDA statement "Caution: New Drug—Limited by Federal law to investigational use". Thus, the drugs would be blinded to both the patients and to the investigators. Only the unblinded Clinical Research Coordinator (CRC) will have access to the randomization scheme and will have the knowledge of the dispensed drugs. To avoid any bias, the principal investigator would strongly advise the study technicians not to communicate any information regarding the 2 drugs to their investigator colleagues.

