Initial data characteristics will be compared between groups using chi-square for categorical variables and t-test or Wilcoxon rank sum test for continuous variables. Change in pain from baseline will be compared between two treatment groups using chi-square test for binary variable and t-test or equivalent non-parametric test for continuous variable, as appropriate. The significance level of the test will be targeted at $\alpha=0.05$ (one sided). Non-inferiority will be established, at the 0.05 significance level if the lower limit of equivalent two-sided 90% confidence interval for the difference in success rate is above non-inferiority margin. Multivariable linear regression analysis will be performed to examine the changes in pain score adjusting potential confounders such as type of pain (lumbar vs. other), prior duration with pain. Reports of side effects will also be investigated between two groups. As an exploratory analysis we will evaluate the time to onset of action between two topical drugs, where time to onset variable will be measured within 1 hour (as \leq 15 min, \leq 30 min, \leq 45 min or \leq 60 min) after the application of drugs at clinic. No adjustments will be made for the multiple endpoints testing. All analyses will be conducted using SAS version 9.4.

Analysis will be performed for the full datasets and by pain group (acute and chronic).

Power Calculation:

Preliminary data to base on power analysis

Meta-analysis from Massey et al (Cochrane Database Syst Rev.; (6) 2014) presented data from combined three studies comparing topical diclofenac versus placebo (Joussellin 2003; Predel 2004; Rowbotham 2003). A total of 319 participants were treated with topical diclofenac, and 307 with placebo. The success rate (i.e. patient reported pain relief at least 50%) was 52% (166/319, range 39% to 92%) for group treated with diclofenac and 25% (77/307, range 8% to 36%) for placebo group.

Assumptions behind power calculations:

There will be two equal-sized treatment arms, one containing diclofenac topical solution 1.5% treated patients and the other Bonipar treated patients. The arms will be compared for a difference in success rate (i.e. pain reduction at least 50% from baseline to follow-up at 1 weeks) with Z-test (one-sided at alpha=0.05) using PASS software. Two scenarios will be considered, as follows:

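### The deciding success-rate comparison is not stratified by acute or chronic pain: a modest, cheaply recovered loss of precision, not a bias

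*Combined protocol and SAP*

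**What the plan says.** All places are in the combined protocol and SAP.

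- **Population (Design & Procedures).** "Individuals who report acute (less than 3 months duration) or chronic musculoskeletal pain of any intensity will be considered for enrollment". Patients come "from Duke Pain Clinic, and selected Duke primary care practices, as well as the Durham VA site". No quota for either pain group is given.
- **Allocation (Dose, Delivery and Dispensing).** Patients are randomised "utilizing a predetermined randomization schedule in a 1:1 ratio". No strata, blocks or minimisation are described.
- **Binary outcome (Data Analysis & Statistical Considerations).** "Change in pain from baseline will be compared between two treatment groups using chi-square test for binary variable". Non-inferiority is shown if the lower limit of the "two-sided 90% confidence interval for the difference in success rate is above non-inferiority margin". No stratified or adjusted form of either is mentioned. The sample size rests on this outcome, "with Z-test (one-sided at alpha=0.05) using PASS software".
- **Where pain duration does enter (same section).** A linear regression of the change in pain score is planned, "adjusting potential confounders such as type of pain (lumbar vs. other), prior duration with pain". Separately, "Analysis will be performed for the full datasets and by pain group (acute and chronic").
- **Baseline data (Baseline Assessments).** Onset of pain is among the items collected before study drug is given.

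**The concern.** The plan treats the acute/chronic distinction as important: it reports by it and lists pain duration as a potential confounder. It uses that information for the continuous outcome but not for the binary one, although the binary outcome carries the margin and sets the sample size.

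If the chance of 50% relief at one week differs between acute and chronic patients, that difference adds variance to the crude comparison, and a stratified comparison would remove it. A visible difference between the arms in acute share would also invite dispute over an unadjusted result. Any adjustment chosen at that stage would be post hoc.

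**Working it through.** **1. Reproduce the plan's figure.** Inputs from Power Calculation: diclofenac 52%, Bonipar 62%, margin 10 points, one-sided alpha 0.05, power 80%. With the null variance taken at 52% and 42%:

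n = [1.645·√(0.52·0.48 + 0.42·0.58) + 0.842·√(0.52·0.48 + 0.62·0.38)]² / 0.20² = 75.8, so 76 per arm, as stated.

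For 52% v 67% the same formula, with 0.25² below the line, gives 48.03, so 49 per arm, also as stated. The sample size stands without stratification.

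**2. Crude power at 76 per arm.** V = 0.52·0.48 + 0.62·0.38 = 0.4852. Power = Φ(0.20/√(0.4852/76) − 1.645) = 80.5%. The 90% half-width is 1.645·√(0.4852/76) = 13.1 points.

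**3. Assumptions.** Let q be the acute share and D the acute-chronic gap in success rate, equal in both arms. The documents give neither. I use q = 0.5, which maximises the effect, and q = 0.2, with D from 10 to 40 points.

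**4. Formulas.**
- SD of the arm difference in acute share: √(2q(1−q)/76). At q = 0.5 this is √(0.5/76) = 8.1 points; at q = 0.2 it is 6.5 points.
- Shift in the crude difference: imbalance × D.
- Stratified variance: V − 2q(1−q)D². For q = 0.5 and D = 0.30 this is 0.4852 − 0.045 = 0.4402, or 91% of V.

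**5. Results at q = 0.5, 76 per arm.**

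| Gap D (points) | Variance v crude | Power, stratified | 90% half-width (points) | Shift at 1 SD (points) | Shift at 95% limit (points) | Chance of shift ≥5 points, either way |
|---|---|---|---|---|---|---|
| 10 | 99% | 80.8% | 13.1 | 0.8 | 1.6 | about 0% |
| 20 | 96% | 81.9% | 12.9 | 1.6 | 3.2 | 0.2% |
| 30 | 91% | 83.7% | 12.5 | 2.4 | 4.8 | 4.0% |
| 40 | 84% | 86.3% | 12.0 | 3.2 | 6.4 | 12.3% |

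At q = 0.2 the stratified power is 80.7%, 81.4%, 82.5% and 84.2%, and the one-SD shift runs from 0.6 to 2.6 points.

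**6. Does the gain need a stratified schedule?** Hardly. If the arms differ by d in acute share at q = 0.5, the information in the stratified estimate is multiplied by about 1 − d². On average d² is 0.081² = 0.0066, which costs about 0.2 points of power.

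**The case against.** **The interval already carries the imbalance.** Chance imbalance under randomisation is part of the sampling variance in the crude interval. The overall one-sided error stays at 5%, and the stated power reproduces without stratifying. This stands. Lost precision and chance imbalance are one cost, not two.

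**The plan does not ignore pain group.** It compares baseline characteristics between arms, analyses acute and chronic patients separately, and adjusts the change score, which is one of the two forms of the primary outcome, for duration. How the schedule was built is simply not described. This also stands. The supportable statement is that no stratification is stated and that the success-rate comparison is unadjusted.

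**The key inputs are assumed.** Neither the acute share nor the gap is in the documents. The range of 39% to 92% success on diclofenac across the cited studies shows that rates vary, but it says nothing about acute against chronic. At a 10-point gap the gain is negligible.

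**A stronger reading.** A reader might infer that imbalance could use up much of the 10-point margin. Given a 30-point gap and an imbalance at its 95% limit in favour of Bonipar, the error conditional on that imbalance is about 13% rather than 5%. With the same imbalance against Bonipar, power is about 61%. These are tail cases that rest on an assumed gap. They describe particular realisations, not the trial's operating characteristics, so the documents do not support that reading.

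What survives is that precision is available at almost no cost, from a variable the plan already considers relevant.

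**Conclusion.** The point holds as a modest efficiency loss. Under the assumptions shown, pre-specified stratification is worth between 0.3 and 6 points of power at 76 per arm with half the patients acute, and up to about 4 points with a fifth acute. A typical chance imbalance moves the crude estimate by roughly 1 to 3 points. A reader might infer bias or an invalid non-inferiority test; the documents support neither. The change is worth making because it is nearly free and settles the adjustment before the data are seen, not because the present analysis is unsound.

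**What to change.** In Data Analysis & Statistical Considerations, name as the primary non-inferiority analysis the two-sided 90% confidence interval for the Mantel-Haenszel risk difference in success, stratified by acute (under 3 months) or chronic pain. Derive the stratum from the pain onset recorded at baseline. Keep the existing margin and the planned analyses by pain group, and report the crude difference with its 90% interval as a sensitivity analysis.

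The cost is a short SAP amendment, made before unblinding. It needs no new data and no more patients.

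Stratifying the randomisation schedule by acute/chronic pain is optional, and only if the schedule is not yet in use. It would require pain group to be recorded before randomisation. Because bottles carry only two labels, permuted blocks within small strata would also make the next label easier to guess. Its benefit would be diluted by dropout. If 240 are consented (120 per arm), 76 per arm complete, losses are random and half are acute, the SD of the imbalance among completers is √[(0.5/76)·(44/119)] = 4.9 points rather than 8.1. Stratifying by site and adding a treatment-by-group interaction estimate are not needed for the gain described here.

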All subjects will be instructed on the application of the assigned drug. Subjects will be asked to apply the study drug 2 pumps 2 times a day to be applied topically on the affected area during a one week treatment period. Application instructions will be provided to the subjects. Prior to the first use, the study coordinator will prime the pump by pushing down fully 4 times, and to discard any solution to ensure an accurate dose is delivered during first use.

Study Drug Application at Home

Written study drug application instructions, storage instructions, and a study diary will be provided to all subjects at the time of discharge from the clinic.

At home, subjects will continue to apply the study drug twice a day. In the 1 week diary, subjects will record daily drug application, pain scores before and after application and any other oral pain medication taken. Subjects are permitted in the study to take acetaminophen (325 to 650 mg tablet up to 4 times a day) if pain persists even with the study drug application.

Subjects will be instructed to observe the following instructions:

1. Please wash and dry hands before and after use.
2. Do not apply to skin with open wounds, or blistered or inflamed areas of the skin.
3. Avoid contact with your eyes and mucous membranes.
4. Do not apply external heat.
5. Do not shower for at least 30 minutes after applying study drug.

6. Do not wear clothing over the treated area until the area is dry.
7. Do not take other NSAID (like aspirin, ibuprofen, naproxen, ketorolac, diclofenac, etc.) while enrolled on this study. Please contact the study doctor or research staff if you are unsure.
8. Keep the bottle away from direct sunlight.
9. Protect the treated area from natural or artificial sunlight.
10. Wait until the treated area is dry before applying sunscreen, insect repellent, lotion, moisturizer or cosmetics to the same area.
11. Avoid skin-to-skin contact between other people and the treated area until the treated area is completely dry.

Follow- Up

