All subjects will be asked to come back for a study visit at one week (+/- 1 day) after initial dosing for assessment, to return the completed diary and remainder of the study drug. If subjects are not able to physically return for the follow-up visit, a remote video follow-up visit can be done for the required study assessments. Remote visits will not be audio or video recorded. Subjects completing a remote video follow-up visit must return to clinic for a physical follow-up visit when able. Subjects who do not receive adequate pain relief during the study may opt to drop out and resume taking their prior prescribed medications or they may return to their primary care physician. If this occurs, subjects will be asked to discard any unused study drug.

DURATION OF STUDY:

This study will be for 1 weeks from initial study drug application.

OUTCOME MEASURES:

The following assessments would be determined:

1. Numerical Pain Rating Scale (NPRS) score at:
 - a. time of enrollment
 - b. 24-hours earlier
 - c. 1 week later twice daily (am and pm)
2. Time of Onset of Action of Bonipar measurement
3. Report of any adverse effects or complications.

Protected health information (PHI) will be kept confidential as required by law. Some information collected about this research study may be kept in a research study record separate from the medical record, and some research information may also be part of the medical record. Except when required by law, subject will not be identified by name, social security number, address, telephone number, or any other direct personal identifier in study records disclosed outside of Duke University Health System (DUHS). For records disclosed outside of DUHS, subject will be identified using a unique code number. The unique code and date of birth will be reported on the Case Report Forms (CRF). The key to the code will be kept in a locked file.

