If the patient is not eligible or does not want to participate in the study their PHI is shredded and destroyed. For consented patient, PHI is kept in research office in a locked desk or cabinet when not being used by the research staff. The information we review are on individual computers which are password protected. The office doors are kept locked when no one from the research staff is in the office. The only people who have access to the rooms are the research staffs which are listed on the key personnel sheet. Study records will be retained with Duke for at least six years after the study is completed.

Selection of Subjects

- List inclusion/exclusion criteria and how subjects will be identified.

INCLUSIONARY CRITERIA:

1. Subject with acute and chronic localized musculoskeletal pain
2. Ages 18 to 80 years
3. Female subjects of childbearing age* must have a negative pregnancy test

Female subjects of childbearing age who are sexually active must agree to use appropriate contraceptive measures for the duration of the study. Medically acceptable contraceptives include: (1) surgical

sterilization (such as tubal ligation or hysterectomy), (2) approved hormonal contraceptives (such as birth control pills, patches, implants or injections), (3) barrier methods (such as a condom or diaphragm) used with a spermicide, or (4) an intrauterine device (IUD).

4. Willing to provide written informed consent
5. Patients taking opioid or NSAID for their musculoskeletal pain may be included if pain is inadequately controlled

*A woman of childbearing age is post-menarche and premenopausal, physiologically capable of fertilization and pregnancy.

EXCLUSIONARY CRITERIA:

1. Use of any topical agents on the affected area within 3 days of screening
2. Subject with active skin lesions or active skin disease or with current cutaneous manifestations of systemic illnesses
3. Subject with known uncontrolled diabetes at time of screening (A1C of more than 9)
4. Subject with uncontrolled hypertension at time of screening (SBP > 160 and DBP > 95)
5. Subject with active uncontrolled GERD (defined as more than 2 episodes per week) or history of peptic ulcer disease
6. Subject with active cancer or active spinal cord lesions
7. Recent spine surgery (within 3 months of screening)
8. Subject with allergies to diclofenac or to other non-steroid anti-inflammatory drugs (NSAID)
9. Known allergies to any oils, methyl salicylate and/or camphor
10. Subject is pregnant or lactating

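### Other pain-relieving topicals are barred before screening but not during the treatment week, and the diary as described would not record them (minor)

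*Combined protocol and SAP*

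**What the plan says.** The rule on other topicals is an entry criterion. Exclusion 1 (Selection of Subjects) reads "Use of any topical agents on the affected area within 3 days of screening".

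For the treatment week, the section Study Drug Application at Home gives 11 numbered instructions. Three bear on this point:

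- Instruction 7: "Do not take other NSAID (like aspirin, ibuprofen, naproxen, ketorolac, diclofenac, etc.) while enrolled on this study".
- Instruction 4: "Do not apply external heat".
- Instruction 10, the only one about putting other products on the treated area: "Wait until the treated area is dry before applying sunscreen, insect repellent, lotion, moisturizer or cosmetics to the same area".

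The same section allows acetaminophen for persisting pain and describes the diary: "subjects will record daily drug application, pain scores before and after application and any other oral pain medication taken".

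Under Follow-Up, "All subjects will be asked to come back for a study visit at one week (+/- 1 day) after initial dosing for assessment". There is also an exit route: "Subjects who do not receive adequate pain relief during the study may opt to drop out and resume taking their prior prescribed medications". Neither the outcome measures nor Data Analysis & Statistical Considerations adds a rule or a record for other topical treatment.

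**The concern.** The sponsor evidently regards another topical on the affected area as a problem, since it keeps a patient out of the trial. Yet the restriction lapses once treatment starts and the outcome is being measured. Subjects have musculoskeletal pain, and the protocol itself expects that pain may persist despite study drug. Reaching for a rub or patch is a foreseeable response.

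This is a non-inferiority trial on a 50% pain-reduction responder rate. If added topical treatment turns some failures into successes equally in both arms, the two rates move closer together. If Bonipar is truly worse, that slightly helps a non-inferiority claim. If Bonipar is truly better, as the sample size assumes, it costs a little power. If use differs between arms, the result can shift either way.

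Under the protocol text such use would not be a deviation. Without a record it could not be counted, compared by arm or examined in a sensitivity analysis.

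**Working it through.** **Reading the text.** What each provision covers:

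| Provision | Period | Reaches a non-NSAID analgesic topical? |
|---|---|---|
| Exclusion 1 | Within 3 days of screening | Yes, at entry only |
| Instruction 7 | While enrolled | No, NSAIDs only |
| Instruction 4 | Treatment week | No, external heat |
| Instruction 10 | Treatment week | No analgesic named; a drying rule for five kinds of skin product |
| Diary, as described | Treatment week | No, other oral pain medication only |

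No row both applies in the treatment week and reaches such a product.

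**Inputs from Power Calculation.** Success 52% on diclofenac and 62% on Bonipar, margin -10 points, one-sided alpha 0.05, 76 per arm.

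**The plan's own figure.** With unpooled variance,

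n = (1.645 + 0.842)² × (0.62×0.38 + 0.52×0.48) / (0.62 - 0.52 + 0.10)² = 75 per arm.

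The pooled-variance form gives 75.5, rounded up to 76. The stated 76 reproduces, and this point does not dispute it.

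**Model for added topical use.** Let u be the share of failures who add a product and k the share of those users who become successes. The observed success rate is

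p* = p + (1 - p) × u × k.

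The documents give neither u nor k, so both are assumptions. For k, the preliminary data say that success "was 52% (166/319, range 39% to 92%) for group treated with diclofenac and 25% (77/307, range 8% to 36%) for placebo group". Topical diclofenac therefore converts (52 - 25)/75 = 36% of those who would fail on placebo. That is probably generous for a non-NSAID product, so half of it (18%) is also shown.

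Example at the margin with u = 0.20 and k = 0.36 in both arms: Bonipar 0.42 + 0.58×0.072 = 0.4618; diclofenac 0.52 + 0.48×0.072 = 0.5546. The difference shrinks from -0.100 to -0.093.

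**Equal use.** Exact enumeration of two binomials, 76 per arm. Non-inferiority is claimed if the lower limit of the unpooled Wald two-sided 90% interval exceeds -0.10.

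| u, both arms | k | False claim, true 42% v 52% | Power, true 62% v 52% |
|---|---|---|---|
| 0 | – | 0.0498 | 0.8001 |
| 0.10 | 0.18 | 0.0523 | 0.7945 |
| 0.20 | 0.18 | 0.0549 | 0.7891 |
| 0.30 | 0.18 | 0.0575 | 0.7837 |
| 0.10 | 0.36 | 0.0549 | 0.7891 |
| 0.20 | 0.36 | 0.0601 | 0.7786 |
| 0.30 | 0.36 | 0.0653 | 0.7693 |

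If the true rates are equal at 52%, the chance of claiming non-inferiority is 0.342 with or without equal use. If Bonipar is far worse (25% v 52%), the false-claim rate is 0.0003 at u = 0.30, k = 0.36.

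**Unequal use, true 42% v 52%.**

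| u Bonipar v diclofenac | k = 0.36 | k = 0.18 |
|---|---|---|
| 0.20 v 0.10 | 0.0902 | 0.0678 |
| 0.10 v 0.20 | 0.0348 | 0.0418 |

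**A harsher assumption.** Suppose instead that the added product abolishes the between-arm difference entirely in a share of all subjects, with diclofenac held at 52%. By normal approximation, shares of 10%, 20% and 30% give false-claim rates of 0.064, 0.081 and 0.101. Power at the planning scenario falls from 0.805 to 0.767, 0.725 and 0.680. This is best read as an outer bound: it needs complete loss of the treatment contrast in a sizeable share of the trial.

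**The case against.** The case against rests on inference, size and value.

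- **The text may imply a bar.** Acetaminophen is the one add-on analgesic named as permitted, unrelieved subjects are offered an exit, instruction 10 lists only non-analgesic products, and Exclusion 1 shows an intent to keep the site clear. This supports treating the gap as one of drafting. But these are implications. None tells a subject not to use a menthol or capsaicin product, and the advice in instruction 7 to ask staff if unsure concerns NSAIDs.
- **The subject-facing documents are not shown.** The diary form and the written application instructions may already cover this. That stands, and it limits the point to the protocol text.
- **The numbers are assumption on assumption.** True. With equal use and 18% conversion the changes are fractions of a percentage point in error rate and under two points in power. The 9.0% needs an assumed 2:1 imbalance in a trial that blinds patients and investigators; the mirror case gives 3.5%. Neither is a forecast.
- **A record changes little by itself.** The analysis section makes no use of the oral medication already in the diary, and permitted acetaminophen and continuing opioids could dilute the contrast in the same way. That is fair for the diary line taken alone. The instruction, however, changes conduct, and acetaminophen at least falls under an existing diary item, whereas topical use falls under none.

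**Conclusion.** The concern holds as a minor one. On the protocol text, non-NSAID analgesic topicals are neither barred nor recorded during the week in which the outcome is measured. With equal use by 10% to 30% of failures and 18% to 36% conversion, the false non-inferiority rate at the margin goes from 5.0% to 5.2%–6.5%. Power at the planning scenario goes from 80.0% to 79.5%–76.9%. Unequal use gave 3.5% to 9.0% in the cases tried, in either direction. All usage and conversion shares are assumptions.

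The one-week treatment period and the option to drop out also limit the effect. The stronger reason to act is that, without an instruction and a record, the trial could not show that such use was rare. Confidence is medium because the diary form and instruction sheet are not available.

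**What to change.** 1. Add one home instruction, for example: *Do not use any other pain-relieving topical product on the affected area until your 1-week visit.*
2. Reword the diary item to cover any other pain medication or topical pain product used, with the date, and confirm it with one question at the existing 1-week visit.

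If the written instructions and diary form already say this, bring the protocol text into line with them.

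The cost is one instruction, one diary line and one question. Sample size, visit schedule and analysis do not change. The downside is one more restriction on subjects and a slightly longer diary.
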